3.2 Discussion and Rationale for Study Design

3.2.1 Study Design

This is the first formal clinical study of rovalpituzumab tesirine in combination with an inhibitor of PD-1 and CTLA-4. Cohort 1 will first assess the tolerability of doublet rovalpituzumab tesirine and nivolumab, a PD-1 inhibitor; if tolerated, Cohort 2 will assess the tolerability of triplet rovalpituzumab tesirine, nivolumab, and ipilimumab; if tolerated, Cohort 3 will assess the tolerability of the triplet with a higher dose of ipilimumab. Expanded enrollment to each cohort may occur in order to explore further the tolerability of one or more regimen(s).

The evaluation of the study endpoints will inform the safety profile of rovalpituzumab tesirine in combination with nivolumab with or without ipilimumab, and may provide evidence of antitumor activity that could influence the trial design of subsequent studies in SCLC.

3.2.2 Method of Assigning Subjects to Cohorts

Upon approval of subject registration by the sponsor or designee, the subject will be enrolled to a cohort. The enrollment confirmation will be documented in the clinical trial master file.

3.2.3 Rationale for Selection of Doses

In a recent Phase 1 study with rovalpituzumab tesirine, the MTD was established at 0.4 mg/kg q3wk based on the incidence of Cycle 1 toxicities, while the recommended Phase 2 dose (RP2D) in SCLC was chosen as 0.3 mg/kg q6wk based on the toxicity and efficacy profile during multiple cycle dosing (AbbVie data on file).

In an ongoing Phase 1 study, nivolumab 3 mg/kg q2wk, and nivolumab 1 mg/kg + ipilimumab 3 mg/kg q3wk, were found to be tolerated in SCLC ([Antonia, 2015](#)). Since the toxicities of these therapies have been generally non-overlapping, the starting dose regimens in this study will therefore be rovalpituzumab tesirine 0.3 mg/kg q6wk + nivolumab 360 mg q3wk, rovalpituzumab tesirine 0.3 mg/kg q6wk + nivolumab 1 mg/kg q3wk + ipilimumab 1 mg/kg q3wk, and rovalpituzumab tesirine 0.3 mg/kg q6wk + nivolumab 1 mg/kg q3wk + ipilimumab 3 mg/kg q3wk. In all dose levels, nivolumab will be administered at 480 mg q4wk when used as a single agent or after 2 cycles at 360 mg in Cohort 1.

3.2.4 Rationale for Nivolumab and Ipilimumab Combination Dose and Schedule

In CA209004, a Phase 1B dose-escalation study of nivolumab in combination with ipilimumab in subjects with unresectable stage III or IV malignant melanoma, the 3 mg/kg nivolumab and 3 mg/kg ipilimumab cohort exceeded the MTD per protocol. While both Cohort 2 (1 mg/kg nivolumab + 3 mg/kg ipilimumab) and Cohort 2a (3 mg/kg nivolumab + 1 mg/kg ipilimumab) had similar clinical activity, a dose of 3 mg/kg of ipilimumab q3wk for a total of four doses and 1 mg/kg nivolumab q3wk for four doses followed by nivolumab 3mg/kg q2wk until progression was chosen. Exposure-response analysis of nivolumab monotherapy across dose ranges of 1 mg/kg to 10 mg/kg reveals similar clinical activity while exposure-response analysis of 0.3 mg/kg, 3 mg/kg, and 10 mg/kg of ipilimumab monotherapy have demonstrated increasing activity with increase in dose in the phase 2 study CA184022 ([Wolchok, 2009](#)). Therefore, theoretically the selection of 3 mg/kg of ipilimumab (Cohort 2) may be more clinically impactful than selection of 3 mg/kg of nivolumab (Cohort 2a).

Data from the phase III study CA209067 in subjects with advanced melanoma showed that the administration schedule of 1 mg/kg of nivolumab q3wk plus 3 mg/kg of ipilimumab q3wk for 4 doses, followed by 3 mg/kg of nivolumab q2wk for cycle 3 and beyond is safe and well tolerated (Larkin, 2015). As described above, current data from study CA209032 showed safety and tolerability of this treatment schedule in heavily pretreated SCLC subjects.

3.2.5 Nivolumab Flat Dose Regimens

The safety and efficacy of 240 mg q2wk flat dose of nivolumab is similar to 3 mg/kg q2wk dosing regimen. A flat dose of nivolumab 240 mg q2wk was selected since it is identical to a dose of 3 mg/kg for subjects weighing 80 kg, the observed median body weight in nivolumab treated cancer patients. The 240 mg q2wk flat dose of nivolumab was recently approved by the FDA. Using a population pharmacokinetic (PPK) model, the overall distributions of nivolumab exposures (C_{avgss} , C_{minss} , C_{maxss} , and C_{min1}) are comparable after treatment with either 3 mg/kg or 240 mg nivolumab. The predicted range of nivolumab exposures (median and 90% prediction intervals) resulting from a 240 mg flat dose across the 35 to 160 kg weight range is maintained well below the corresponding exposures observed with the well tolerated 10 mg/kg nivolumab q2wk dosage. Across the various tumor types in the clinical program, nivolumab has been shown to be safe and well tolerated up to a dose level of 10 mg/kg, and the relationship between nivolumab exposure produced by 3 mg/kg and efficacy and safety has been found to be relatively flat. Given the similarity of nivolumab PK across tumor types and the similar exposures predicted following administration of 240 mg flat dose compared to 3 mg/kg q2wk regimen, it is expected that the safety and efficacy profile of 240 mg q2wk nivolumab will be similar to that of 3 mg/kg nivolumab.

3.2.6 Blinding

This is not a blinded trial.

4. Study Population

Subjects must meet all of the enrollment criteria to be eligible for this study. Eligibility criteria may not be waived by the investigator and are subject to review in the event of Good Clinical Practice (GCP) audit and/or appropriate health regulatory authority inspection.

To be eligible for retreatment as described in Section 3.1.2, subjects must meet all inclusion and none of the exclusion criteria outlined in this section.

4.1 Inclusion Criteria

- 1) Written informed consent.
 - a) Must have signed and dated an IRB/IEC approved written informed consent form (ICF) in accordance with regulatory and institutional guidelines. This must be obtained before the performance of any protocol-related procedures that are not part of normal patient care.
 - b) Must be willing and able to comply with scheduled visits, treatment schedule, laboratory testing, and other requirements of the study.
- 2) Target population
 - a) Histologically or cytologically confirmed extensive-stage SCLC with PD after at least one platinum-based chemotherapeutic regimen.
 - b) Measurable disease, defined as at least 1 tumor lesion ≥ 10 mm in the longest diameter or a lymph node ≥ 15 mm in short-axis measurement assessed by computerized tomography (CT) scan (RECIST v1.1) or evaluable disease.
 - c) Availability of representative baseline tumor tissue (archived or on-study biopsy) suitable for immunohistochemistry testing. Up to the first 12 subjects of each study cohort must be DLL3 positive per IHC (Immunohistochemistry) assay criteria, based on central assessment prior to enrollment.
 - d) ECOG performance status of 0 or 1. See Appendix 13.3 for conversion of performance status using Karnofsky scales, if applicable.
 - e) Minimum life expectancy of at least 12 weeks.

- f) Asymptomatic central nervous system (CNS) metastases, if present, must be stable, with or without previous treatment, in the absence of corticosteroids for at least 2 weeks prior to initiation of study drugs.
 - g) Recovery to Grade 1 of any clinically significant toxicity (excluding alopecia) prior to initiation of administration of study drugs.
 - h) Satisfactory laboratory parameters:
 - i. Absolute neutrophil count (ANC) $\geq 1,000/\mu\text{L}$.
 - ii. White blood cell count (WBC) $\geq 2,500/\mu\text{L}$.
 - iii. Platelet count $\geq 100,000/\mu\text{L}$.
 - iv. Hemoglobin ≥ 9.0 g/dL.
 - v. Total bilirubin ≤ 1.5 x upper limit of normal (ULN) or ≤ 3 x ULN for subjects with Gilbert's disease.
 - vi. Alanine aminotransferase (ALT) and aspartate aminotransferase (AST) ≤ 3.0 x ULN (≤ 5 x ULN if evidence of hepatic involvement by malignant disease).
 - vii. Creatinine ≤ 1.5 x ULN or estimated glomerular filtration rate (eGFR) ≥ 40 mL/min/1.73m².
 - viii. Albumin ≥ 3 g/dL.
 - iv. Lipase ≤ 1.5 x ULN. Subjects with Lipase > 1.5 x ULN may enroll if there are neither clinical nor radiographic signs of a pancreatitis.
 - x. Amylase ≤ 1.5 ULN. Subjects with Amylase > 1.5 x ULN may enroll if there are neither clinical nor radiographic signs of a pancreatitis
 - i) At least two (2) weeks since last dose of any prior systemic anticancer therapy (e.g. chemotherapy, radiation, and/or surgery).
- 3) Age and Reproductive Status
- a) Adult 18 years of age or older.
 - b) If female, subject must be either postmenopausal, defined as:
 - Age > 55 years with no menses for 12 or more months without an alternative medical cause.
 - Age ≤ 55 years with no menses for 12 or more months without an alternative medical cause AND an FSH level > 40 IU/L.
- OR

- Permanently surgically sterile (bilateral oophorectomy, bilateral salpingectomy, or hysterectomy)

OR

- Woman of Childbearing Potential practicing at least one protocol specified method of birth control, starting at Day 1 through at least 31 weeks following the last dose of study drugs (Section 5.10).
- c) If the subject is male and is sexually active with female partner(s) of childbearing potential, he must agree, from Day 1 through 31 weeks following last dose of study drugs, to practice the protocol specified methods of contraception (Section 5.10).
- d) Females of childbearing potential must have a negative serum pregnancy test result at Screening and a negative urine pregnancy test prior to dosing on Day 1. Females of non-childbearing potential (either postmenopausal or permanently surgically sterile as defined in Section 5.10) at Screening do not require pregnancy testing.

4.2 Exclusion Criteria

A subject will not be eligible for study participation if he/she meets any of the following criteria:

- 1) Prior treatment with or exposure to:
 - a) A pyrrolobenzodiazepine (PBD)-based drug (including rovalpituzumab tesirine unless undergoing retreatment in the context of this protocol)
 - b) Other monoclonal antibodies
 - c) ADCs
 - d) Radioimmunoconjugates
 - e) T-cell or other cell-based or biologic therapies
 - f) Experimental anti-tumor vaccines; therapies that target any T cell co-stimulation or checkpoint pathways, such as anti-PD-1, anti-PD-L1, anti-PD-L2, anti-CD137, or anti CTLA-4 antibody, including ipilimumab; or other medicines specifically targeting T cells.
- 2) Any significant medical condition, including any condition suggested by screening laboratory findings that, in the opinion of the investigator or sponsor, may place the subject at undue risk from the study and/or may interfere with interpretation of study results.
- 3) Documented history of a cerebral vascular event (stroke or transient ischemic attack), unstable angina, myocardial infarction, or cardiac symptoms consistent with New York Heart Association (NYHA) Class III–IV (Appendix 13.4) within 6 months prior to their first dose of study drugs.

- 4) Recent or ongoing serious infection, including:
 - a) Any active grade 3 or higher (per NCI CTCAE version 4.03) viral, bacterial, or fungal infection within 2 weeks of the first dose of the study drugs. Routine antimicrobial prophylaxis is permitted.
 - b) Known seropositivity for or active infection by human immunodeficiency virus (HIV).
 - c) Active hepatitis B (by surface antigen expression or polymerase chain reaction [PCR]) or active hepatitis C (by PCR) infection, or subjects taking hepatitis-related antiviral therapy within 6 months of first dose of study drugs.
- 5) Previous malignancies (except non-melanoma skin cancers, and the following in situ cancers: bladder, gastric, colon, endometrial, cervical/dysplasia, melanoma, or breast) unless a complete remission was achieved at least 2 years prior to study entry AND no additional therapy is required during the study period.
- 6) Active, known, or suspected autoimmune disease. Vitiligo, type I diabetes mellitus, residual hypothyroidism only requiring hormone replacement, psoriasis not requiring systemic treatment, or conditions not expected to recur in the absence of an external trigger are permitted.
- 7) A condition requiring systemic treatment with corticosteroids (>10 mg daily prednisone equivalent) or other immunosuppressive medications within 14 days prior to administration of study drugs. Inhaled or topical steroids and adrenal replacement doses >10 mg daily prednisone equivalent are permitted in the absence of active autoimmune disease.
- 8) Female subject who is pregnant, breastfeeding, or is considering becoming pregnant during the study or for approximately 31 weeks after the last dose of study drugs.
- 9) Male subject who is considering fathering a child or donating sperm during the study for approximately 31 weeks after the last dose of study drugs.
- 10) Prior participation in a rovalpituzumab tesirine clinical trial, or known hypersensitivity to rovalpituzumab tesirine or excipient contained in the drug formulation, unless undergoing retreatment with rovalpituzumab tesirine in the context of this protocol.
- 11) Known hypersensitivity to any corticosteroid or excipients contained in the drug formulations.

4.3 Removal of Subjects from Therapy or Assessment

The sponsor or its designee must be notified if a subject is withdrawn from study treatment or from the study. The reason(s) for withdrawal must be documented in the subject's medical records and electronic case report form (eCRF). When a subject withdraws from treatment, all

safety data normally required at the end of the study (i.e. the End of Treatment (EOT) Visit and long-term follow-up [LTFU]) will be obtained if possible (Sections 6.5 and 6.6).

4.3.1 Discontinuation of Study Drug(s)

Treatment with study drug(s) may be discontinued for any of the following reasons:

- PD
- AE
- Investigator decision
- Subject decision, Non-AE
- Other

4.3.2 Subject Discontinuation from Study

Any subject may be discontinued from the study for any of the following reasons:

- Subject withdrawal of consent
- AE
- Death
- Investigator decision
- Lost to follow-up
- Significant noncompliance to protocol
- Study termination by sponsor

5. Treatments

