Tumor response will be assessed according to the imaging schedule in Section 6.4.6. Treatment decisions by the investigator will be based on RECIST v1.1.

Subjects will be eligible to continue treatment until unacceptable toxicity, progressive disease (PD), withdrawal of consent, study termination, or completion of a planned course of treatment (if a regimen with a limited number of doses is selected), whichever occurs first. Subjects who discontinue study treatment prior to PD will be evaluated for response q6wk until 24 weeks, then q12wk until disease progression or initiation of new anticancer treatment, whichever occurs first, and will afterwards be followed for survival until death or study termination, whichever occurs first.

Blood samples for PK, immunogenicity, biomarker and PD assessments will be collected at protocol-defined time points to support the study endpoints (Sections 7.3 and 7.4).

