6.6 Long-Term Follow-up; Every 6-12 weeks \pm 1 week

For all subjects who discontinue study drugs for reasons other than disease progression (e.g. due to an AE), the first follow-up visit will occur at 6 weeks (\pm 1 week) after the last dose of study drugs, then q6wk (\pm 1 week) until 6 months, then q12wk (\pm 1 week) until disease progression, initiation of new anticancer therapy, or withdrawal/ termination from the study. Procedures to be conducted on follow-up visits include:

- Record AEs and SAEs (Section 7.6)
- Disease response assessment consisting of CT scans of the chest, abdomen, and pelvis (and neck if indicated) (Section 7.2)
- MRI of the brain – if clinically indicated (e.g. if CNS progression has been documented previously). CT of the brain with IV contrast may be substituted at the discretion of the investigator (Section 7.2).
- (Optional) fresh tumor tissue, collected at disease progression (Section 7.4.1)
- Blood samples for:
 - Blood soluble markers (Section 7.4.3)

Survival status will be followed until death or study withdrawal/termination, whichever occurs first.

At progression, an optional collection of fresh tumor tissue may be conducted (Section 7.4.1).

After disease progression, subjects who are not retreated will be followed for subsequent anticancer therapies and dates, as well as survival status, q6wk (\pm 1 week) for 24 weeks (6 months), then q12wk (\pm 1 week) until death or study termination, whichever occurs first.

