7.6 Adverse Event Collection

All AEs reported from the time of study drug administration until 100 days following discontinuation of study drug administration will be collected, whether solicited or spontaneously reported by the subject. In addition, protocol-related serious and non-serious AEs will be collected from the time the subject signed the study-specific informed consent.

Serious and non-serious AEs occurring after the study-specific informed consent is signed but prior to the initial dose of study drug will be collected **only** if they are considered by the investigator to be causally related to the study-required procedures.

AE information will be collected as shown in [Figure 2](#).

Figure 2. Adverse Event Collection

*Only if considered by the investigator to be causally related to study-required procedures.

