			Day -14 to -1	Day -1		Day 1 (±2 d)	Day 2 ¹	Day 8 ³ (±2 d)	Day 15 ³ (±2 d)			
	Circulating Tumor Cells ⁴⁴					X ⁴⁵					X	
	Genotyping ⁴⁶		X									
	Serosal Fluid ⁴⁷					X		X		X		
	Cell Free Circulating Tumor DNA (ctDNA) ⁴⁸					X					X	

Table Notes

* **Cycles 1 – 3 are 3 weeks. Cycles 4 and beyond are 4 weeks.**

- 1) Only applies to Cycle 1 and Cycle 3 when rovalpituzumab tesirine is administered.
- 2) EOT occurs within 7 days of documentation of the decision to discontinue treatment.
- 3) Visits on Days 8 and 15 should be done during Cycles 1 and 3 only (may be omitted during cycles that do not include rovalpituzumab tesirine).
- 4) LTFU includes the 100 day follow up for safety; LTFU also occurs q6wk (±1 week) until 6 months, then q12wk (±1 week) until disease progression, initiation of new anticancer therapy, or withdrawal/termination from the study. Disease/Response Assessment consists of subsequent anticancer therapies and dates, date of progression (if not already captured on study), and survival status. Subjects will be followed for survival until death or study termination, whichever occurs first. After disease progression, subjects who are not retreated will be followed (Section 6.6).
- 5) This may be a telephone follow-up or performed in clinic.
- 6) Prescreening ICF only.
- 7) Informed consent for the main portion of this study will be obtained prior to the performance of any study procedures and may occur within 30 days prior to the Day 1 Visit. All other screening procedures must occur within 14 days prior to Day 1.
- 8) Confirmation of study eligibility per inclusion/exclusion criteria.
- 9) Medical and Surgical History includes descriptions of conditions or procedures, and dates of onset - offset.
- 10) Malignancy History includes tumor type, stage, sites of metastases, mutational status.
- 11) Prior Anticancer Treatments include names of specific treatments, dates of administration, response to therapy, and DOR, if known.

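### Section 4.3.2 allows study exit for AE, investigator decision or noncompliance without withdrawal of consent, and Section 6.6 conflicts with Section 3.1 and Appendix 13.1 on whether survival follow-up then continues

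*Combined protocol and SAP*

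**What the plan says.** The protocol separates stopping drug from leaving the study. Section 4.3.1 begins "Treatment with study drug(s) may be discontinued for any of the following reasons" and lists, among others, AE and investigator decision. Section 4.3.2 begins "Any subject may be discontinued from the study for any of the following reasons", repeats those two, and adds "Significant noncompliance to protocol".

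The end of survival follow-up is stated in two ways:

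- Section 6.6: "Survival status will be followed until death or study withdrawal/termination, whichever occurs first".
- Section 3.1, for subjects who stop treatment before progression: they "will afterwards be followed for survival until death or study termination, whichever occurs first". The schedule notes for all three cohorts in Appendix 13.1 agree: "Subjects will be followed for survival until death or study termination, whichever occurs first". The last paragraph of Section 6.6, on subjects after progression who are not retreated, also names only death or study termination.

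The LTFU visits in Section 6.6, at which AEs are recorded, stop at progression, new anticancer therapy, or withdrawal or termination from the study. Section 6.7 has survival status recorded at the end of study only if it can be obtained.

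On safety, Section 7.6 says "All AEs reported from the time of study drug administration until 100 days following discontinuation of study drug administration will be collected". Sections 8.1.1.1 and 8.2.2.6 use the same window. The introduction to Section 4.3 asks for EOT and LTFU safety data, where possible, from a subject who withdraws from treatment. It has no matching sentence for a subject who leaves the study.

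**The concern.** A subject who leaves for an AE, by investigator decision or for noncompliance has not refused further contact. Vital status and late AEs could still be collected. Under Section 4.3.2 and the Section 6.6 sentence, however, a site may stop survival contacts for that subject; under Section 3.1 and Appendix 13.1 it may not. Sites can therefore act differently on the same protocol.

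Two of the three reasons, AE and investigator decision, are plausibly linked to prognosis. If such subjects are censored alive at exit, the Kaplan-Meier OS estimate treats them as having the same later risk as those who remain. If their risk is higher, OS is overstated. On safety, which is the primary objective, the remainder of the 100-day window would depend on unscheduled contact.

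**Working it through.** **1. The passages side by side.**

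| Question | Section 6.6, survival sentence | Section 3.1, last paragraph of 6.6, Appendix 13.1 notes |
|---|---|---|
| Survival follow-up ends at death? | Yes | Yes |
| At study termination? | Yes | Yes |
| At the subject's withdrawal from the study? | Yes | Not named |

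For a subject who leaves under Section 4.3.2 with consent intact, the left column stops survival follow-up and the right column continues it. Section 4.3 does not settle the matter, because it covers withdrawal from treatment only. Section 10.3.4 gives Kaplan-Meier medians for OS, states no censoring rule, and leaves details to the SAP.

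**2. AE window.** The window is 100 days from the end of study drug. LTFU visits fall at 6-week steps, so days 42 and 84 lie within it. If participation ended at the EOT visit, taken here as 7 days after the last dose (an assumption), 100 − 7 = 93 days and both visits would have no assured scheduled contact.

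**3. Possible effect on OS, as illustration only.** The plan gives no figure to reproduce.

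Inputs:
- Median OS 7.7 months (Section 1.2, earlier Phase 1 study, DLL3-high subjects). Exponential survival is assumed, so λ = ln 2 / 7.7 = 0.0900 per month and 12-month OS = exp(−12λ) = 34.0%.
- A fraction f marked for exit, at a time uniform over 0 to 3 months (assumed). f = 6% and 11% are borrowed from Section 1.3, where they are treatment discontinuations for treatment-related AEs in another study. f = 20% is assumed.
- Death hazard after exit multiplied by h (assumed 1, 2 or 3).

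If exits are censored, everyone still at risk has hazard λ, so Kaplan-Meier tends to 34.0% at 12 months and a median of 7.7 months whatever f and h are. With full follow-up, for t ≥ 3 months and h > 1,

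S(t) = (1 − f)·exp(−λt) + f·exp(−λht)·[exp(3λ(h−1)) − 1] / [3λ(h−1)].

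For f = 11%, h = 2, t = 12: 0.89 × 0.3395 + 0.11 × 0.1323 = 0.3167.

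| f | h | True 12-month OS | True median (months) | Median overstated by (months) |
|---|---|---|---|---|
| any | 1 | 34.0% | 7.70 | 0 |
| 6% | 2 | 32.7% | 7.42 | 0.3 |
| 6% | 3 | 32.2% | 7.26 | 0.4 |
| 11% | 2 | 31.7% | 7.20 | 0.5 |
| 11% | 3 | 30.8% | 6.92 | 0.8 |
| 20% | 2 | 29.8% | 6.83 | 0.9 |
| 20% | 3 | 28.2% | 6.34 | 1.4 |

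A simulation of 1,000,000 subjects per scenario agrees to within about 0.02 months for the medians and 0.1 percentage points at 12 months.

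**4. Without a hazard assumption.** With 30 subjects in a cohort, k early exits with unknown vital status leave 12-month survival bounds k/30 wide: 7, 10 and 20 percentage points for k = 2, 3 and 6.

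**The case against.** The case against is substantial, and most of it stands against a stronger claim.

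- A reader might infer that the 100-day AE window is cut short. The documents do not say so. Sections 7.6, 8.1.1.1 and 8.2.2.6 tie it to the end of drug, whatever the study status. The Appendix 13.1 notes mention the 100-day safety follow-up separately from the 6- to 12-weekly visits that stop at withdrawal.
- A reader might infer that a site can close out a subject with an unresolved serious AE and still comply. Section 8.1 requires AEs to be followed to a satisfactory conclusion. Section 8.2.2.6 requires each SAE to be followed to a defined endpoint and names only withdrawal of consent as a barrier to learning its outcome.
- A reader might infer that an AE ends participation. Section 4.3.2 is permissive, and Section 6.6 sends subjects who stop drug for an AE into LTFU.
- A reader might infer that OS is in fact informatively censored. That requires such exits to happen and to be prognostic, and no censoring rule is stated. The Section 6.6 sentence is the outlier among several that continue survival follow-up.
- The 11% is a treatment-discontinuation rate from another study, not a rate of leaving this one. Even at that rate, the shift of 2 to 3 points in 12-month OS is about a third of the binomial standard error with 30 subjects, √(0.34 × 0.66 / 30) = 8.6 points. OS is descriptive under a secondary objective, and the benchmark named in Section 1.4 for advancing the programme is ORR.

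What remains is the contradiction on survival follow-up and the absence of any statement on scheduled contact after a study exit with consent intact.

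**Conclusion.** The point holds as an inconsistency and a gap. Section 4.3.2 allows three kinds of study exit that do not involve withdrawal of consent. Section 6.6 can be read to end survival contacts for those subjects, against Section 3.1 and Appendix 13.1. The 100-day AE window stays in force, but no scheduled contact is assured to fill it. OS may be informatively censored, and late AEs may be missed, if such exits occur and relate to prognosis.

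The size is unknown. Under the assumptions shown, median OS would be overstated by 0.3 to 0.8 months at 6% to 11% marked for exit, by 0.9 to 1.4 months at 20%, and not at all if risk after exit is unchanged. These figures illustrate direction and order of size; they do not predict bias in this trial. The correction is worth making because it is cheap and because data lost after a subject is closed out may not be recoverable.

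**What to change.** State in Sections 4.3.2 and 6.6 that a subject discontinued from the study for AE, investigator decision or noncompliance, who has not withdrawn consent to follow-up, continues:

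- survival-status contacts until death or study termination;
- AE collection through 100 days after the last study drug;
- LTFU scans only up to the limits already in Section 6.6, namely progression or new anticancer therapy.

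Reword the Section 6.6 survival sentence to match Section 3.1 and Appendix 13.1, with withdrawal of consent to follow-up as the one exception. Leave the treatment-discontinuation list in Section 4.3.1 as it is.

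The cost is protocol wording and a few follow-up contacts that the schedule already contains.
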